#### Rationale:

The purpose of this study is to evaluate the safety of intramuscular (IM) administration of Engensis in Participants with Amyotrophic Lateral Sclerosis (ALS) as compared to Placebo. Safety will be assessed by incidences of treatment-emergent adverse events (TEAEs), treatment-emergent serious adverse events (TESAEs), injection site reactions (ISRs) and other adverse events of special interest (AESIs), and the clinically significant laboratory values after injections for Engensis compared to Placebo. Exploratory endpoints include assessment of muscle function using the Revised Amyotrophic Lateral Sclerosis Functional Rating Scale (ALSFRS-R) and ALSFRS-R subscores for Fine and Gross Motor Function; muscle strength by quantitative testing using Handheld Dynamometry (HHD) and the Accurate Test of Limb Isometric Strength (ATLIS) where available; quality of life using the ALS Assessment Questionnaire (ALSAQ-40); patient global impression of change (PGIC), and clinical global impression of change (CGIC); and evaluation of lung function using Slow Vital Capacity (SVC). Muscle biopsies will be performed during the study for future biomarker analyses.

Engensis contains the active pharmaceutical ingredient VM202, a novel genomic complementary deoxyribonucleic acid (cDNA) hybrid human hepatocyte growth factor (HGF) coding sequence (HGF-X7) expressing two isoforms of HGF, HGF728 and HGF723, being developed for treatment of ALS.

Data from Helixmith's first clinical trial in ALS, the Phase 1/2 ALS study (VMALS-001), which included 18 Participants who were followed for 9 months, suggested that targeted delivery of HGF to motor neurons via intramuscular (IM) injections of Engensis was safe and well-tolerated. Safety assessments during the study included reports of 79 adverse events (AEs) in 17 Participants (94.4%), including 26 mild injection site reactions (Grade 1). Five SAEs were reported in 3 Participants. Only injection site reactions were considered related to study treatment. Following injections until Day 90, a plateau or a relative slowing in decline of the ALSFRS-R scores and muscle strength was noted, suggesting a slowing of disease progression. After 90 days, the plateau was no longer observed in the ALSFRS-R, with the notable exception of a trend toward better preservation of bulbar and breathing functions as measured by the ALSFRS-R.

---

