### **8.5.4. Adverse Events of Special Interest**

#### **Categories of AESIs**

There are three main categories of AESIs as presented below: 1) those considered to be related to the angiogenesis potential of Engensis, 2) other medical problems in this patient population, and 3) injection site reactions.

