#### **8.5.4.2. Other Medical Problems in ALS Patients**

Several medical problems are frequently observed in patients with ALS that should be considered AESIs. These medical problems are listed below.

- Pulmonary Medical Problems: Because patients with ALS are at an increased risk to develop pulmonary medial problems such as aspiration of food or liquids, pneumonia,

---

and respiratory arrest, all events of this type that occur after randomization will be considered AESIs.

- **Progressive Muscle Weakness:** Because some patients with ALS may develop rapidly progressive muscle weakness that results in loss of ability to care for self, decubitus ulcers, or weight loss due to impaired deglutition, all events of this type that occur after randomization will be considered AESIs.
- **Bulbar Disease:** Participants may develop bulbar disease or worsening on bulbar disease following randomization manifested as challenges with dysarthria, facial weakness, impaired tongue pulsion or palate elevation, and impaired mastication and swallowing; all of these types of events that occur after randomization will be considered AESIs.

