- This definition is not intended to include experiences of relatively minor medical significance such as uncomplicated headache, nausea, vomiting, diarrhea, influenza, and accidental trauma (e.g., sprained ankle), which may interfere with or prevent everyday life functions but do not constitute a substantial disruption.

QMD Ref: Worldwide-TMP-ST-005-7.0 Effective: 12Aug2019	Governing QMD: Worldwide-SOP-ST-001
Confidentiality Statement	

This document is the property of Worldwide Clinical Trials Inc. and may not be duplicated, copied, altered or removed from company without prior approval from Worldwide Quality Assurance or in compliance with Worldwide Standard Operating Procedures.

Worldwide Clinical Trials Controlled Quality Management Document			
 WORLDWIDE CLINICAL TRIALS	Sponsor:	Helixmith Co., Ltd.	
Protocol Number:			VMALS-002-2
STATISTICAL ANALYSIS PLAN VERSION 3.0			

- e Is a congenital anomaly/birth defect
- f Other situations:
 - Medical or scientific judgment should be exercised in deciding whether SAE reporting is appropriate in other situations such as important medical events that may not be immediately life-threatening or result in death or hospitalization but may jeopardize the Participant or may require medical or surgical intervention to prevent one of the other outcomes listed in the above definition. These events should usually be considered serious.
 - Examples of such events include invasive or malignant cancers; intensive treatment in an emergency room or at home for allergic bronchospasm, blood dyscrasias, or convulsions that do not result in hospitalization; or development of drug dependency or drug abuse.

Treatment-Emergent Serious Adverse Event (TESAE)

- A serious event that emerges during treatment, having been absent at pretreatment, or worsens relative to the pretreatment state, as defined in the EP Guidance.
- The TESAE is not related to causality / drug relatedness. It may or may not be related to the drug but is considered a TESAE due to its appearance at or after the treatment has been administered.

Adverse Events of Special Interests (AESI)

There are 4 main categories of AESIs that will be considered in the study:

1. Related to the angiogenesis potential of Engensis
 - Atherosclerosis
 - Cancer
2. Other medical problems in this patient population
 - Pulmonary Medical Problems
 - Progressive Muscle Weakness
 - Bulbar Disease
3. Injection site reactions
4. COVID-19 infections

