The following tables will be presented:

- Summary of TEAE (Table 14.3.1.1)

QMD Ref: Worldwide-TMP-ST-005-7.0 Effective: 12Aug2019	Governing QMD: Worldwide-SOP-ST-001
Confidentiality Statement	

This document is the property of Worldwide Clinical Trials Inc. and may not be duplicated, copied, altered or removed from company without prior approval from Worldwide Quality Assurance or in compliance with Worldwide Standard Operating Procedures.

Worldwide Clinical Trials Controlled Quality Management Document			
 WORLDWIDE CLINICAL TRIALS	Sponsor:	Helixmith Co., Ltd.	
	Protocol Number:	VMALS-002-2	
STATISTICAL ANALYSIS PLAN VERSION 3.0			

- TEAEs organized by SOC and PT (Table 14.3.1.2)
- TESAEs organized by SOC and PT (Table 14.3.1.3)
- TEAEs organized by SOC and PT and Maximum Severity (Table 14.3.1.4)
- TEAEs organized by SOC and PT and Maximum Relationship (Table 14.3.1.5)
- TESAEs organized by SOC and PT and Maximum Severity (Table 14.3.1.6)
- TESAEs organized by SOC and PT and Maximum Relationship (Table 14.3.1.7)
- Incidence Injection site reactions by SOC and PT (Table 14.3.1.8)
- Incidence of clinically significant laboratory values (Table 14.3.1.9)
- AESIs organized by SOC and (Table 14.3.1.10)
- TEAEs leading to study discontinuation by SOC and PT (Table 14.3.1.11)
- TESAEs leading to study discontinuation by SOC and PT (Table 14.3.1.12)
- TEAEs leading to study drug withdrawal by SOC and PT (Table 14.3.1.13)
- TESAEs leading to study drug withdrawal by SOC and PT (Table 14.3.1.14)
- TEAEs related to study medication by SOC and PT (Table 14.3.1.15)
- TESAEs related to study medication by SOC and PT (Table 14.3.1.16)

The following listings will be provided:

- All AEs (Listing 16.2.7.1)
- AESIs (Listing 16.2.7.2)
- TESAEs (Listing 16.2.7.3)
- Injection Site Reactions (Listing 16.2.7.4)
- TEAEs leading to study discontinuation (Listing 16.2.7.5)
- TEAEs related to study medication (Listing 16.2.7.6)
- TESAEs leading to death (Listing 16.2.7.7)

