14.3.1.10	Adverse Events of Special Interest by System Organ Class and Preferred Term – Safety Analysis Population	IP	
14.3.1.11	Treatment-Emergent Adverse Events leading to study discontinuation by System Organ Class and Preferred Term – Safety Analysis Population	IP	
14.3.1.12	Treatment-Emergent Serious Adverse Events leading to study discontinuation by System Organ Class and Preferred Term – Safety Analysis Population	IP	14.3.1.2
14.3.1.13	Treatment-Emergent Serious Adverse Events leading to study drug withdrawal by System Organ Class and Preferred Term – Safety Analysis Population	IP	14.3.1.3
14.3.1.14	Treatment-Emergent Serious Adverse Events leading to study drug withdrawal by System Organ Class and Preferred Term – Safety Analysis Population	IP	
14.3.1.15	Treatment-Emergent Adverse Events related to study medication by System Organ Class and Preferred Term – Safety Analysis Population	IP	14.3.1.10
14.3.1.16	Treatment-Emergent Serious Adverse Events related to study medication by System Organ Class and Preferred Term – Safety Analysis Population	IP	
14.3.3	Narratives of Deaths, Other Serious and Certain Other Significant Adverse Events		
14.3.4	Abnormal Laboratory Values		
14.3.4.1	Serum Chemistry – Safety Analysis Population	IP	
14.3.4.2	Serum Chemistry, Shift Table – Safety Analysis Population	IP	
14.3.4.3	Hematology – Safety Analysis Population	IP	14.3.4.1
14.3.4.4	Hematology, Shift Table – Safety Analysis Population	IP	14.3.4.2
14.3.5	Exposure to Study Drug		
14.3.5.1	Performed injections – Safety Analysis Population	IP	
14.3.5.2	Amount of Performed Injections – Safety Analysis Population	IP	

QMD Ref: Worldwide-TMP-ST-005-7.0 Effective: 12Aug2019

Governing QMD: Worldwide-SOP-ST-001

Confidentiality Statement

This document is the property of Worldwide Clinical Trials Inc. and may not be duplicated, copied, altered or removed from company without prior approval from Worldwide Quality Assurance or in compliance with Worldwide Standard Operating Procedures.

Worldwide Clinical Trials Controlled Quality Management Document			
 WORLDWIDE CLINICAL TRIALS	Sponsor:	Helixmith Co., Ltd.	
	Protocol Number:	VMALS-002-2	
STATISTICAL ANALYSIS PLAN VERSION 3.0			

Table Number	Table Title	Validation Method	Shell Number (if repeat)
14.3.5.2	Administered volume of Engensis – Safety Analysis Population	IP	
14.3.5.3	Treatment Compliance – Safety Analysis Population	IP	
14.3.6	Vital Signs and Physical Examination		

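### The SAP defines AESI categories but tabulates AESIs only by SOC and PT, so apart from injection site reactions no planned output gives participants per category

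*SAP*

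**What the plan says.** The protocol synopsis (Rationale) says that safety will be assessed by the incidence of several kinds of event, among them "injection site reactions (ISRs) and other adverse events of special interest (AESIs". Protocol 8.5.4 opens with "There are three main categories of AESIs as presented below": angiogenesis-related events (atherosclerosis, cancer), other medical problems in ALS patients (pulmonary, progressive muscle weakness, bulbar), and injection site reactions.

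SAP 6.14.1 carries these over with their sub-categories and adds COVID-19: "There are 4 main categories of AESIs that will be considered in the study".

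The planned outputs are then as follows.

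- One AESI summary table, written in 6.14.1 as "AESIs organized by SOC and (Table 14.3.1.10". The second classifier is missing. SAP Section 11 supplies it in the title: "Adverse Events of Special Interest by System Organ Class and Preferred Term – Safety Analysis Population".
- One table for a single category: "Incidence Injection site reactions by SOC and PT (Table 14.3.1.8".
- One participant-level listing: "AESIs (Listing 16.2.7.2". The SAP does not say whether it shows the category.

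No table or figure in 6.14.1 or Section 11 is described as organised by AESI category or sub-category.

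**The concern.** The plan sets up a classification and then does not use it. A reader who wants to know how many participants per arm had, say, at least one pulmonary AESI is given rows by SOC and PT instead. Those rows count participants within a term. A category count is the number of distinct participants across all the terms in the category, and one participant can appear in several rows.

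Safety is the primary objective, and Protocol 9.3.1 rules out formal testing, so the descriptive tables are the result. Events of one clinical kind recorded under different terms would appear as separate small rows, with no line that brings them together.

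There is also a gap before the counting starts: neither document gives a rule, term list or data field that assigns an event to a category. If this is settled only after unblinding, it is settled with treatment known.

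**Working it through.** The documents give no event rates and no figure for this point, so there is nothing to reproduce beyond the arm sizes. The check is whether the planned rows determine the category count.

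**Inputs.** Protocol 5.3: 18 participants at 2:1, so 18 × 2/3 = 12 Engensis and 18 × 1/3 = 6 Placebo. The PT counts below are assumed, for illustration only.

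**Formula.** If a category covers k PTs with participant counts c1, …, ck in an arm of size n, the number D of distinct participants satisfies

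max(c1, …, ck) ≤ D ≤ min(n, c1 + … + ck).

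**Results.**

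- Engensis, three PTs with 2, 2 and 1: max = 2 and min(12, 5) = 5. Complete enumeration for n = 12 confirms that 2, 3, 4 and 5 are all possible. For example, {A,B}, {A,B}, {A} gives 2 people, and {A,B}, {C,D}, {E} gives 5. The incidence is 2/12 = 16.7% to 5/12 = 41.7% (exact 95% intervals 2.1% to 48.4% and 15.2% to 72.3%).
- Engensis, five PTs with 1 each: 1 to 5 people, 8.3% to 41.7%.
- Placebo, three PTs with 1 each: 1 to 3 of 6, 16.7% to 50.0%.
- One PT with 2: exactly 2/12 = 16.7%. The count can be read off.

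Setting the first and third cases side by side, the Engensis minus Placebo difference could lie anywhere from 16.7 − 50.0 = −33.3 points to 41.7 − 16.7 = +25.0 points. In that example the table does not fix even its sign.

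**When the table is enough.** The count can be recovered if a category is recorded under a single PT, or if its terms make up exactly one SOC row of the AESI table. Cancer or COVID-19 might be such cases. The documents contain no mapping of terms to SOCs, so which categories qualify cannot be settled from them.

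**Which rows to combine.** Protocol 8.5.4.2 puts "loss of ability to care for self, decubitus ulcers, or weight loss due to impaired deglutition" under progressive muscle weakness, while impaired swallowing stands under bulbar disease. A swallowing problem with weight loss could therefore go to either category or to both. Protocol 8.5.4.1 also leaves a judgement, since it turns on diagnoses suggesting recent coronary disease. Without a stated rule, two readers could combine different rows.

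**The case against.** Several points on the other side stand.

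- A reader might infer that effects on breathing, bulbar function or strength cannot be compared between arms. The documents do not support that. SAP 6.15 summarises SVC, the ALSFRS-R bulbar and motor subscores, HHD and ATLIS by treatment group, and plans Kaplan-Meier displays for tracheostomy and death. Only the AESI category incidence is absent.
- A reader might infer that the information is lost. It is not. SAP 6.3 has all data listed, Listing 16.2.7.2 covers AESIs, and with 18 participants a hand count is feasible. SAP Section 6 also allows further tables in the study report. The table shells are not in the documents, and the rows of Table 14.3.1.1 are not described, so the most that can be said is that no category count is specified.
- A reader might infer that every category is scattered over several SOCs, by design. Neither document says so. The bound above needs only more than one PT and no matching SOC row.
- A reader might infer that a weight-loss term could not be placed because a PT does not show its cause. That is weak. Table 14.3.1.10 holds only events already judged to be AESIs, and Protocol 8.5.4 names weight loss under one category only. The overlap over swallowing is the better example.
- AESIs other than injection site reactions are not listed primary endpoints (Protocol 9.3.1). Injection site reactions are, and they have their own table and listing. The ALS-related categories are AESIs because such problems are frequent in ALS; the protocol gives a mechanistic reason only for the angiogenesis-related ones.

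These points limit the size of the problem but do not remove it. A hand count from a listing that may not show the category depends on the reader's own assignment, and a table added later is not prespecified. A single row for any AESI would not help much either, because injection site reactions are AESIs. They made up 26 of the 79 adverse events in the earlier ALS study (Protocol 1.1), and each dosing visit here involves 128 injections.

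**Conclusion.** The point holds as a reporting gap that should be closed before database lock. The SAP defines four AESI categories with sub-categories, but its only AESI summary is by SOC and PT. Apart from injection site reactions, no specified output gives participants per arm with at least one angiogenesis-related, pulmonary, muscle-weakness, bulbar or COVID-19 event. For a category with more than one PT and no matching SOC row, the count is not determined by the table; in the illustration it ranges from 2 to 5 of 12 (16.7% to 41.7%).

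This rests on the table title in SAP Section 11, because the line in 6.14.1 is incomplete, and on assumed PT counts. It does not mean that data are missing, that a listed primary endpoint goes unreported, or that any test or decision rule changes.

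**What to change.** In SAP 6.14.1 and Section 11:

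- Change Table 14.3.1.10 to show, by arm, participants (n, %) with at least one event in each AESI category and sub-category (atherosclerosis, cancer, pulmonary, progressive muscle weakness, bulbar, injection site reactions, COVID-19). Count each participant once per level, and keep SOC and PT nested below.
- Assign each AESI to its category in a blinded review before database lock. State a rule for events that fit more than one category, in particular swallowing problems.
- Show the assigned category in Listing 16.2.7.2.
- Complete the unfinished table line in 6.14.1 so that it agrees with the title in Section 11.

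The cost is SAP wording, one revised table shell, one listing column and a short blinded review for 18 participants. No new data collection is needed.

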6.14.2 Laboratory Data

QMD Ref: Worldwide-TMP-ST-005-7.0 Effective: 12Aug2019	Governing QMD: Worldwide-SOP-ST-001
Confidentiality Statement	

This document is the property of Worldwide Clinical Trials Inc. and may not be duplicated, copied, altered or removed from company without prior approval from Worldwide Quality Assurance or in compliance with Worldwide Standard Operating Procedures.

Worldwide Clinical Trials Controlled Quality Management Document			
 WORLDWIDE CLINICAL TRIALS	Sponsor:	Helixmith Co., Ltd.	
Protocol Number:			VMALS-002-2
STATISTICAL ANALYSIS PLAN VERSION 3.0			

Laboratory data consists of results of following examinations: serum chemistry, hematology, coagulations and urine pregnancy test.

Serum chemistry will include the following variables:

- Sodium
- Potassium
- Chloride
- Bicarbonate
- Calcium
- Inorganic Phosphate
- Magnesium
- Glucose
- Amylase
- Lipase
- Lactate Dehydrogenase
- Blood Urea Nitrogen (BUN)
- Creatine Kinase (CK)
- Creatinine
- Aspartate Aminotransferase (AST)
- Alanine Aminotransferase (ALT)
- Alkaline Phosphatase
- Gamma-Glutamyl Transpeptidase (GGT)
- Total Bilirubin
- Total Protein
- Albumin

Hematology will include the following variables:

- White Blood Cells Count
- Hemoglobin
- Hematocrit
- Platelet Count
- Neutrophils Count

Serum chemistry and hematology analyses will be performed at Screening, Day 60 pre-dose, Day 120 pre-dose and End of Study.

QMD Ref: Worldwide-TMP-ST-005-7.0 Effective: 12Aug2019	Governing QMD: Worldwide-SOP-ST-001
Confidentiality Statement	

This document is the property of Worldwide Clinical Trials Inc. and may not be duplicated, copied, altered or removed from company without prior approval from Worldwide Quality Assurance or in compliance with Worldwide Standard Operating Procedures.

Worldwide Clinical Trials Controlled Quality Management Document			
 WORLDWIDE CLINICAL TRIALS	Sponsor:	Helixmith Co., Ltd.	
Protocol Number:			VMALS-002-2
STATISTICAL ANALYSIS PLAN VERSION 3.0			

Measured values of serum chemistry and hematology analyses and their changes from baseline, will be presented with descriptive statistics at each visit by treatment group (Tables 14.3.4.1 and 14.3.4.3). Incidence of clinically significant values and shift tables by the clinical significance based on laboratory assessments will be presented for each parameter (Tables 14.3.1.9, 14.3.4.2, 14.3.4.4). Percentages for each parameter will be based on the number of participants who have at least one measurement for at baseline and at corresponding post-baseline visit.

Result of urine pregnancy test is variable with two possible values: positive / negative. The test should be performed only for women with childbearing potential at Screening, Day 0 pre-dose and End of Study. Urinalysis will be presented only in a listing.

Results of serum chemistry, hematology and urine pregnancy tests will be listed (Listings 16.2.8.1 – 16.2.8.3).

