#### 9.3.1. Primary Endpoints

Safety analyses in this study will evaluate the safety profile of Engensis as compared with Placebo. The primary endpoints for safety are as follows:

- Incidence of TEAEs and TESAEs for Engensis compared to Placebo
- Incidence of injection site reactions for Engensis compared to Placebo
- Incidence of clinically significant laboratory values for Engensis compared to Placebo

No formal statistical testing will be conducted for the safety analyses. All Participants in the safety subset will be included in these analyses. Participants will be grouped by treatment received. All summaries will be derived based on available data. No imputation will be performed for missing values. All safety analyses will be made on the Safety Population.

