#### 10.2.5. Recording and Follow-Up of AE/TEAE and/or SAE/TESAE

AE and SAE Recording

• When an AE/TEAE or SAE/TESAE occurs, it is the responsibility of the Investigator to review all documentation (e.g., hospital progress notes, laboratory reports, and diagnostics reports) related to the event.

• The Investigator will then record all relevant AE/TEAE or SAE/TESAE information in the eCRF.

• It is not acceptable for the Investigator to send photocopies of the Participant’s medical records to the Sponsor or designee in lieu of completion of the AE/SAE eCRF page.

---

- Instances may arise when copies of medical records for certain cases are requested by the Sponsor or designee. In this case, all Participant identifiers, with the exception of the Participant number, will be redacted on the copies of the medical records before submission to the Sponsor or designee.
- The Investigator will attempt to establish a diagnosis of the event based on signs, symptoms, and/or other clinical information. Whenever possible, the diagnosis (not the individual signs/symptoms) will be documented as the AE/SAE.

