3 ENDPOINTS

3.1 Primary Endpoint

- Incidence of treatment-emergent adverse events (TEAEs) and treatment-emergent serious adverse events (TESAEs) for Engensis compared to Placebo
- Incidence of injection site reactions for Engensis compared to Placebo
- Incidence of clinically significant laboratory values for Engensis compared to Placebo

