11 LIST OF TABLES, FIGURES AND LISTINGS

Table Number	Table Title	Validation Method	Shell Number (if repeat)
14.1	Demographics Data		
14.1.1	Disposition		
14.1.1.1	Subject Disposition – All Participants Population		
14.1.1.2	Participant Visits – Safety Analysis Population		
14.1.2	Demographics		
14.1.2.1	Demographic and Baseline Characteristics – Safety Analysis Population		
14.1.3	Baseline Characteristics		
14.1.3.1	ALS History – Safety Analysis Population	IP	
14.1.3.2	Prior Medical History - Safety Analysis Population	IP	
14.1.3.3	Ongoing Medical History - Safety Analysis Population	IP	14.1.3.2
14.1.3.4	Familial Cancer History – Safety Analysis Population	IP	
14.2	Efficacy Data		
14.3	Safety Data		
14.3.1	Displays of Adverse Events		
14.3.1.1	Summary of Adverse Events – Safety Analysis Population	IP	
14.3.1.2	Treatment Emergent Adverse Events by System Organ Class and Preferred Term – Safety Analysis Population	IP	
14.3.1.3	Treatment Emergent Serious Adverse Events by System Organ Class and Preferred Term – Safety Analysis Population	IP	
14.3.1.4	Treatment Emergent Adverse Events by System Organ Class and Preferred Term and Maximum Severity – Safety Analysis Population	IP	
14.3.1.5	Treatment Emergent Adverse Events by System Organ Class and Preferred Term and Maximum Relationship – Safety Analysis Population	IP	
14.3.1.6	Treatment Emergent Serious Adverse Events by System Organ Class and Preferred Term and Maximum Severity – Safety Analysis Population	IP	
14.3.1.7	Treatment Emergent Serious Adverse Events by System Organ Class and Preferred Term and Maximum Relationship – Safety Analysis Population	IP	

QMD Ref: Worldwide-TMP-ST-005-7.0 Effective: 12Aug2019	Governing QMD: Worldwide-SOP-ST-001
Confidentiality Statement	

This document is the property of Worldwide Clinical Trials Inc. and may not be duplicated, copied, altered or removed from company without prior approval from Worldwide Quality Assurance or in compliance with Worldwide Standard Operating Procedures.

Worldwide Clinical Trials Controlled Quality Management Document			
 WORLDWIDE CLINICAL TRIALS	Sponsor:	Helixmith Co., Ltd.	
	Protocol Number:	VMALS-002-2	
STATISTICAL ANALYSIS PLAN VERSION 3.0			

Table Number	Table Title	Validation Method	Shell Number (if repeat)
14.3.1.8	Incidence of Injection Site Reactions – Safety Analysis Population	IP	
14.3.1.9	Incidence of Clinically Significant Laboratory Values – Safety Analysis Population	IP	14.3.1.3

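### The SAP specifies the table for the third primary endpoint (clinically significant laboratory values, Table 14.3.1.9) inconsistently, and no reading of it yields a study-level incidence

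*SAP*

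**What the plan says.** SAP 3.1 names the endpoint: "Incidence of clinically significant laboratory values for Engensis compared to Placebo". Three places in the SAP deal with its table.

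- **SAP 6.14.2 (Laboratory Data)** is the only text that describes the content: "Incidence of clinically significant values and shift tables by the clinical significance based on laboratory assessments will be presented for each parameter". It cites Table 14.3.1.9 together with shift tables 14.3.4.2 and 14.3.4.4. The percentages that follow are "based on the number of participants who have at least one measurement for at baseline and at corresponding post-baseline visit".
- **SAP 6.14.1 (Adverse Events)** includes it in the list of adverse event tables. The entry begins "Incidence of clinically significant laboratory values (Table 14.3.1.9" and, unlike the injection site reaction entry just above it, mentions no coding hierarchy.
- **SAP Section 11** lists "Incidence of Clinically Significant Laboratory Values – Safety Analysis Population" under the adverse event displays. In the column for repeated shells it gives 14.3.1.3, whose title is "Treatment Emergent Serious Adverse Events by System Organ Class and Preferred Term – Safety Analysis Population".

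Two other rules bear on the table. SAP 6.2.14 tabulates only scheduled post-baseline values; repeat, unscheduled and early termination assessments go to listings. Protocol 9.3.1 says "All Participants in the safety subset will be included in these analyses", and also that summaries use the data available, without imputation.

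**The concern.** A programmer cannot follow both 6.14.2 and Section 11. Rows by laboratory parameter and rows by coded event term are different tables built from different data, and they need not count the same participants. The endpoint itself asks for something simpler: in each arm, how many participants had a clinically significant laboratory value after injection. Neither description states that figure. Because the primary analysis is descriptive, the printed counts and percentages are the result. If the definition is settled after the data are seen, it can affect what is reported for a primary safety endpoint.

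**Working it through.** The plan gives no figure for this endpoint. The only number to reproduce is the allocation: 18 × 2/3 = 12 Engensis and 18 × 1/3 = 6 Placebo, as stated in Protocol 5.3. All event and missing-data counts below are assumptions chosen to show scale.

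**1. Can one table satisfy all three places?** SAP 6.14.2 lists 21 chemistry and 5 hematology variables, so a per-parameter table has 21 + 5 = 26 parameter rows. The layout of 14.3.1.3 has rows by System Organ Class and Preferred Term. The two cannot be reconciled in one shell.

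**2. Do the two layouts count the same participants?** They overlap by design, because Protocol 10.2.1 makes a laboratory result judged clinically significant an adverse event. They can still differ:

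- Protocol 10.2.5 states: "Whenever possible, the diagnosis (not the individual signs/symptoms) will be documented as the AE/SAE". A flagged value that belongs to a diagnosis may then not appear under a laboratory term.
- Under SAP 6.14.1 an event is treatment-emergent only if it emerged or worsened from the day of first dosing. A value already clinically significant at baseline and unchanged is still a flagged value, but not a treatment-emergent event.

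Illustration of the second route: two participants in an arm have a flagged value, and one of them was flagged and unchanged from baseline.

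- Engensis: laboratory count 2/12 = 16.7%; treatment-emergent count 1/12 = 8.3%.
- Placebo: 2/6 = 33.3% against 1/6 = 16.7%.

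**3. If 6.14.2 governs, is there a study-level incidence?** Chemistry and hematology are scheduled at three post-baseline visits (Days 60, 120 and 180). If the percentages follow the visit-paired denominator, there are 26 × 3 = 78 of them per arm and no summary row. The participant-level figure cannot be recovered from these. Suppose two parameters are each flagged in 2 of 12 Engensis participants. The number of participants affected could be 2 (2/12 = 16.7%), 3 (3/12 = 25.0%) or 4 (4/12 = 33.3%).

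**4. What does SAP 6.2.14 remove?** Protocol 7.2 calls for chemistry and hematology at early termination. Take a participant who leaves before Day 60 with a clinically significant result only at that visit, and no other flagged values in the arm. This participant drops out of both numerator and denominator.

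- Engensis: 0/11 = 0.0% in the table, against 1/12 = 8.3% if the result is counted.
- Placebo: 0/5 = 0.0% against 1/6 = 16.7%.

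**5. How much does the denominator alone matter?** With one flagged participant and m others lacking the visit's value, the percentage is 100 × 1/(n − m).

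| m | Engensis, n = 12 | Placebo, n = 6 |
|---|---|---|
| 0 | 8.3% | 16.7% |
| 1 | 9.1% | 20.0% |
| 2 | 10.0% | 25.0% |
| 3 | 11.1% | 33.3% |

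**The case against.** The best defence is that there is only one definition. SAP 6.14.2 alone says what the table contains. The adverse event version rests on where the table is filed and on one layout reference, and that list has other slips: 14.3.1.13 and 14.3.1.14 share a title, 14.3.5.2 appears twice, and 14.6.9 names itself as its shell. Taken literally, the reference would restrict the endpoint to serious events, which is hardly intended. This stands. It would be too strong to say that the SAP words two rival definitions; the fault is an inconsistent specification, possibly clerical.

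Two further inferences are tempting and not supported.

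- A reader might argue that ALS-related findings are excluded as adverse events (Protocol 10.2.1) but counted as laboratory values. Protocol 8.2.6 applies the same exclusion, with the same exception for unexpected severity, to clinically significant laboratory findings themselves. That route to different counts falls away.
- A reader might say that Protocol 9.3.1 requires the Safety Population N as denominator. It names who is included but sets no percentage base, and its available-data rule fits a denominator of participants with results. Likewise, no denominator is stated for the adverse event tables beyond the general rule in SAP 6.3.

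It is also fair that large amounts of missing data are assumed, not documented. In the earlier ALS study 17 of 18 participants completed nine months (Protocol 2.2.6.1). All laboratory results and adverse events are to be listed, so with 18 participants a careful reader could recount. That limits the harm but does not supply the missing primary figure. Nor does the clerical explanation repair the visit-paired denominator, the absent any-parameter row, or the loss of early termination results.

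**Conclusion.** The point holds in this form: Table 14.3.1.9 is specified inconsistently, and even on the most charitable reading the third primary endpoint has no study-level participant incidence. A clinically significant value seen only at an early termination or unscheduled visit would be missing from this primary safety table. One participant counted or not changes an arm's incidence by 1/12 = 8.3 or 1/6 = 16.7 percentage points. A single missing paired value changes a one-participant percentage less, from 8.3% to 9.1% or from 16.7% to 20.0%. These sizes assume the planned 12:6 split; the event and missing counts are illustrative. No sample size or error rate is affected, since no formal safety testing is planned. This should be corrected before database lock.

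**What to change.** In SAP 6.14.2, define Table 14.3.1.9 once:

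- **Numerator:** number and percent of participants with at least one post-injection value flagged clinically significant by the investigator, for any parameter (headline row) and then by parameter.
- **Visits:** count early termination and unscheduled results for this table, as a stated exception to SAP 6.2.14.
- **Baseline status:** show values already clinically significant at baseline separately from new ones.
- **Denominator:** participants with at least one post-injection result (for the parameter, in the parameter rows), with the Safety Population N displayed beside it. This is consistent with the available-data rule in Protocol 9.3.1.

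Keep the visit-paired denominator for shift tables 14.3.4.2 and 14.3.4.4 only. In Section 11, replace the shell reference 14.3.1.3 with a shell that has parameter rows. Laboratory findings coded as adverse events stay in Table 14.3.1.2.

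The cost is a paragraph of SAP text and one table shell. No new data are needed, since chemistry and hematology are already collected at the scheduled and early termination visits.
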